4.2.2 Rationale for Dose Selection/Regimen

Both VARIVAXTM PE34 process and VARIVAXTM (2016 commercial product) are administered subcutaneously as a 0.5-mL dose. The dose of VARIVAXTM PE34 process is the same as for VARIVAXTM (2016 commercial product) because VARIVAXTM PE34 is formulated in such a way to contain the same minimum potency at the time of release.

All subjects enrolled in this trial will receive 2 doses of trial vaccine administered concomitantly with M-M-R[™] II. This is consistent with the recommended regimens in the United States and European Union (EU). In the United States, the ACIP recommends a 2-dose regimen of varicella vaccines. A minimum interval of 3 months (90 days) is recommended between each dose of VZV-containing vaccines when administered to children. In the EU, at least 1 month must elapse between the first and second dose of any live viral attenuated vaccine. In both the United States and the EU, varicella vaccine can be administered to children as a 2-dose series. In regions where vaccination of toddlers against varicella is the standard of care, VZV-containing vaccines are typically administered concurrently with measles-mumps-rubella-containing vaccines.

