5.1.3 Subject Exclusion Criteria

The subject must be excluded from participating in the trial if the subject:

- *If the subject meets any of the exclusion criteria marked with an asterisk (*), the Day 1 visit may be rescheduled for a time when these exclusion criteria are no longer met; however, the subject would only be permitted to continue with a delayed vaccination if the visit can be performed within 7 days of consent.
 - 1. Has received any measles-, mumps-, rubella-, or VZV-containing vaccine, either alone or in any combination, at any time before the trial, or is anticipated to receive any of these vaccines, either alone or in any combination, during the trial.

- Has any congenital or acquired immune deficiency, neoplastic disease, or depressed immunity, including those resulting from corticosteroid use (see Exclusion Criterion #3 and Section 5.5 – Concomitant Medications) or other immunosuppressive therapy.
- 3. Has received 1) systemic immunomodulatory steroids (no more than the equivalent of 2 mg/kg total daily dose of prednisone or >20 mg/day of prednisone or equivalent for subjects weighing >10 kg) for more than 7 consecutive days within 3 months before entering trial, or 2) any dose of systemic immunomodulatory steroids within 7 days before entering trial, or 3) is expected to require systemic immunomodulatory steroids during the course of the trial.

Exception: Subjects who require nonsystemic steroids (e.g., topical, ophthalmic, inhaled) will be eligible for vaccination.

- 4. Has any blood dyscrasias, leukemia, lymphomas of any type, or other malignant neoplasms affecting the bone marrow or lymphatic systems.
- 5. Has a history of allergy or anaphylactic reaction to neomycin, gelatin, sorbitol, egg proteins (egg or egg products), chicken proteins, or any component of VARIVAXTM or M-M-RTM II, as stated in the package inserts.
- 6. *Has received salicylates (e.g., aspirin or any aspirin-containing products) within 14 days before vaccination.
- 7. *Has had an exposure to varicella, HZ, measles, mumps, or rubella in the last 4 weeks before trial vaccination involving:
 - a. Continuous household contact, or
 - b. Playmate contact (generally >1 hour of indoor play), or
 - c. Hospital contact (in the same 2- to 4-bed room or in adjacent beds in a large ward or prolonged face-to-face contact with an infectious staff member or patient), or

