These subject exclusion criteria must be reviewed for each subject before Vaccination 2 to ensure that none of the criteria apply to the subject.

The subject must be excluded from receiving Vaccination 2 if the subject:

- 27. Has had any immunoglobulin, nonautologous blood, or blood products administered Postvaccination 1.
- 28. Has had any nontrial measles-, mumps-, rubella-, or VZV-containing vaccine administered Postvaccination 1.
- 29. Has received systemic immunomodulatory steroids (no more than the equivalent of >2 mg/kg total daily dose of prednisone or equivalent or >20 mg/day of prednisone or equivalent for subjects weighing >10 kg) for more than 7 consecutive days Postvaccination 1.
- 30. Has any blood dyscrasias, leukemia, lymphomas of any type, or other malignant neoplasms affecting the bone marrow or lymphatic systems diagnosed Postvaccination 1.
- 31. Has had any acquired or congenital immunodeficiency or active tuberculosis diagnosed Postvaccination 1.
- 32. Has had the occurrence of varicella infection Postvaccination 1.
- 33. Has had a vaccine-related allergic or anaphylactoid reaction reported Postvaccination 1.

- 34. Has enrolled in any other clinical trial other than a surveillance trial Postvaccination 1.
- 35. Has had a seizure, including a febrile seizure, Postvaccination 1.
- 36. Has had thrombocytopenia Postvaccination 1.

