5.5 Concomitant Medications/Vaccinations (Allowed and Prohibited)

Medications or vaccinations specifically prohibited in the exclusion criteria are not allowed during the ongoing trial. If there is a clinical indication for any medication or vaccination specifically prohibited during the trial, discontinuation from trial therapy or vaccination may be required. The investigator should discuss any questions regarding this with the Sponsor Clinical Director. The final decision on any supportive therapy or vaccination rests with the investigator and/or the subject's primary physician. However, the decision to continue the subject on trial therapy or vaccination schedule requires the mutual agreement of the investigator, the Sponsor and the subject's legally acceptable representative.

All medications administered from 30 days before each trial vaccination through 42 days after each trial vaccination should be recorded on the appropriate eCRF. Subjects should not have received any previous measles-, mumps-, rubella-, or VZV-containing vaccines, either alone or in any combination, or any such vaccines outside of trial protocol for the duration of the trial.

Product: V210 Protocol/Amendment No.: A03-01

Subjects should not have received salicylates (e.g., aspirin or any aspirin-containing products) during the 14 days before Vaccination 1, and should not receive these products until after 42 days after Vaccination 2, because the use of salicylates in children with varicella has been associated with Reye syndrome. Subjects must not have received any immunoglobulin, a blood transfusion, or blood-derived products (does not include autologous blood/blood products) for at least 5 months (150 days) before vaccination and should not receive these products while enrolled in this trial, unless there is a medical necessity warranting their use.

Use of immunosuppressive therapies is reason for exclusion, with the following exceptions:

- 1. Use of topical, ophthalmic, and inhaled steroids is permitted.
- 2. Use of systemic immunomodulatory steroids must meet the following criteria:
 - Subjects should not receive any dose of systemic immunomodulatory steroids within 7 days before or after each vaccination.

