 - Subjects should not receive systemic immunomodulatory steroids (no more than the equivalent of 2 mg/kg total daily dose of prednisone or equivalent or >20mg/day of prednisone or equivalent for subjects weighing >10 kg) for more than 7 consecutive days from the time of trial start through the end of the 42-day safety follow-up period Postvaccination 2.

If higher doses of systemic immunomodulatory steroids or other systemic immunosuppressive agents are administered after trial entry but before Vaccination 2, or if the subject otherwise develops an immunosuppressive condition in this interval, then the second dose of trial vaccines should be discontinued.

It is preferable that other vaccines routinely administered to children who are between 12 months to 23 months of age be given outside of the trial period so as not to confound the results from this trial. These vaccines will not be provided by the Sponsor or Sponsor designee. If necessary, enrollment in the trial can be deferred if a medically important vaccine needs to be administered; however, the subject would only be permitted to continue with a delayed vaccination if the visit can be performed within the allowed window. A full 15 days must elapse between the receipt of inactivated nontrial vaccines and enrollment into the trial. A full 31 days must elapse between the receipt of live nontrial vaccines (e.g., yellow fever) and enrollment into the trial.

If medically necessary, both licensed inactivated and live nontrial vaccines may be administered in the interval between Visit 2 and Visit 3. As specified in Section 5.1.3, a minimum of 43 days should elapse between Visit 1 (when the first dose of trial vaccine is administered) and receipt of the inactivated or live nontrial vaccine. In addition:

- If a licensed, inactivated (**nonlive**) vaccine (e.g., IPV, DTaP, Hib) is given between Visits 2 and 3, the second dose of trial vaccine must not be given until at least 15 days have elapsed.
- If a licensed **live** vaccine is given between Visits 2 and 3, the second dose of trial vaccine must not be given until at least 31 days have elapsed.

After the successful completion of trial procedures at Visit 4 (Week 19 [Days 133-147 Postvaccination 1]), both inactivated and live nontrial vaccines may be administered.

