5.8 Subject Withdrawal/Discontinuation Criteria

5.8.1 Discontinuation of Vaccination

Discontinuation of vaccination does not represent withdrawal from the trial.

As certain data on clinical events beyond vaccination discontinuation may be important to the study, they must be collected through the subject's last scheduled follow-up, even if the subject has discontinued vaccination. Therefore, all subjects who discontinue trial vaccination prior to completion of the vaccination period will still continue to participate in the trial as specified in Section 6.0 (Trial Flow Chart) and Section 7.1.5.3 (Discontinued Subjects Continuing to be Monitored in the Trial) unless consent is withdrawn. For subjects who will not receive Vaccination 2, all tasks except vaccination and eVRC should be completed.

Subjects may discontinue vaccination at any time for any reason or be dropped from vaccination at the discretion of the investigator should any untoward effect occur. In addition, a subject may be discontinued from vaccination by the investigator or the Sponsor if vaccination is inappropriate, the trial plan is violated, or for administrative and/or other safety reasons. Specific details regarding procedures to be performed at vaccination discontinuation are provided in Section 7.1.4 – Other Procedures.

A subject must be discontinued from vaccination but continue to be monitored in the trial for any of the following reasons:

- The subject or subject's legally acceptable representative requests to discontinue vaccination.
- The subject has a medical condition or personal circumstance that, in the opinion of the investigator and/or Sponsor, places the subject at unnecessary risk through continued participation in the trial or does not allow the subject to adhere to the requirements of the protocol.
- \circ The subject meets any of the criteria in Section 5.1.3.
- Treatment unblinding.

For subjects who are discontinued from vaccination but continue to be monitored in the trial, all visits and procedures, as outlined in the trial flowchart, except vaccination and eVRC should be completed.

Discontinuation from vaccination is "permanent." Once a subject is discontinued, he/she shall not be allowed to restart vaccination.

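### The systemic-steroid threshold is misworded in three places: criterion 3 and Section 5.5 literally catch low doses and, at 10 kg or less, miss high ones, and criterion 29 contradicts itself

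*Combined protocol and SAP*

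**What the plan says.** **Entry (Section 5.1.3, criterion 3).** The list gives reasons to exclude. Criterion 3 has three parts. Part 1 covers "systemic immunomodulatory steroids (no more than the equivalent of 2 mg/kg total daily dose of prednisone or >20 mg/day of prednisone or equivalent", with the 20 mg limb limited to children over 10 kg. It requires a course of more than 7 consecutive days in the 3 months before entry. Part 2 excludes any systemic dose in the 7 days before entry. Part 3 excludes children expected to need systemic steroids during the trial.

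**Entry (criterion 2).** Depressed immunity is a separate exclusion, but it gives no dose and refers the reader back: "depressed immunity, including those resulting from corticosteroid use (see Exclusion Criterion #3 and Section 5.5".

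**Before the second dose (Section 5.1.3.2, criterion 29).** The child must not receive Vaccination 2 after a course of more than 7 days described as "no more than the equivalent of >2 mg/kg total daily dose of prednisone or equivalent or >20 mg/day of prednisone or equivalent", again with the 20 mg limb for children over 10 kg.

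**During the trial (Section 5.5).** One bullet reads "Subjects should not receive systemic immunomodulatory steroids (no more than the equivalent of 2 mg/kg total daily dose" and continues with the same 20 mg limb and the same duration, from trial start to the end of the 42-day follow-up after Vaccination 2. The next paragraph begins "If higher doses of systemic immunomodulatory steroids or other systemic immunosuppressive agents are administered after trial entry but before Vaccination 2" and says that the second dose should then be stopped.

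**Stopping rule (Section 5.8.1).** One mandatory reason to stop vaccination is "The subject meets any of the criteria in Section 5.1.3".

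**The concern.** An exclusion describes what disqualifies a child. A phrase that sets a ceiling belongs in a description of what is allowed. Placed inside an exclusion, it reverses the 2 mg/kg limb, while the 20 mg limb beside it still points the right way.

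This is the protocol's numeric immunosuppression threshold in a trial where every child receives live vaccines at both vaccination visits. A site that applies the text as written would turn away children after low-dose courses. In one group it would also have no numeric rule against a recent high-dose course. The text used before the second dose cannot be applied literally at all.

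**Working it through.** The plan gives no figure to reproduce here. The check compares the rule as written with the rule evidently meant.

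**Inputs.** Let w be weight in kg and d the daily prednisone-equivalent dose in mg, for a course of more than 7 consecutive days. The limits (2 mg/kg, 20 mg/day, 10 kg) are those of criterion 3 part 1.

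**Rules.**
- As written: caught if d ≤ 2w, or if w > 10 and d > 20.
- As meant: caught if d > 2w, or if w > 10 and d > 20.

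**Weight of 10 kg or less.** The 20 mg limb does not apply. The written rule is d ≤ 2w and the intended rule is d > 2w, so they give opposite answers at every dose.

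**Weight over 10 kg.** Here 2w > 20. Any dose is either at most 2w, and caught by the first limb, or above 2w and therefore above 20 mg, and caught by the second. The written rule catches every dose. The intended rule reduces to d > 20. The two agree only above 20 mg/day.

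| Weight | Dose | mg/kg/day | As written | As meant |
|---|---|---|---|---|
| 10 kg | 20 mg/day | 20/10 = 2.0 | caught | not caught |
| 10 kg | 21 mg/day | 21/10 = 2.1 | not caught | caught |
| 12 kg | 20 mg/day | 20/12 = 1.67 | caught | not caught |
| 12 kg | 21 mg/day | 21/12 = 1.75 | caught | caught |

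The Section 5.5 bullet has the same construction, so the same table applies to it.

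**Criterion 29.** It puts the ceiling phrase in front of a greater-than sign. A dose cannot be at most a quantity defined as more than 2 mg/kg, so this limb has no literal meaning. Without the ceiling phrase, the criterion gives the intended rule.

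**Evidence of the intended direction.** Three places show that higher doses disqualify: the 20 mg limb, the greater-than sign before 2 mg/kg in criterion 29, and the Section 5.5 sentence on higher doses. The first covers only children over 10 kg, the second is spoiled by the phrase before it, and the third gives no number. None states the 2 mg/kg rule correctly.

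**Size of the entry gap.** Part 2 catches any dose in the last 7 days, whatever its size. The gap therefore needs a last dose more than 7 days but within 3 months before entry. If 3 months is taken as 90 days, that is days 8 to 90, or 90 − 7 = 83 days. The 90-day figure is an assumption borrowed from the dose-spacing text in Section 4.2.2 ("A minimum interval of 3 months (90 days) is recommended between each dose"). These are days and dose regions, not numbers of children.

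**The case against.** The best defence is that no competent investigator would be misled. The sentence is ungrammatical, so the reading tested above is one parse among several. The Section 5.5 bullets are introduced as exceptions to a general bar on immunosuppressive therapy, so the phrase may be a leftover permitted ceiling. A rule in which low steroid doses disqualify and high doses do not is clinically implausible. The sentence on higher doses gives the right direction.

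Most of this stands: the intent can be recovered. It does not rescue the wording. Read as a permitted ceiling, the 20 mg limb becomes a ceiling set at more than 20 mg/day, which means nothing. No single reading makes both limbs work, and no correct version exists elsewhere for a site to follow.

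The defence also points to backstops. A child in the gap must still be in good health, be free of depressed immunity (criterion 2), pass the investigator's judgement under criterion 17, and not be expected to need systemic steroids (criterion 3 part 3). After entry, criterion 22 defers the second dose for any systemic steroid in the previous 7 days. This stands, and it makes the gap narrow. It does not close it: criterion 2 sends the reader back to the faulty text for the dose, and criterion 17 concerns interference with the trial objectives.

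The Section 5.8.1 link should not be pressed. Criterion 3 part 1 concerns use before entry, and later courses fall under criterion 29 and Section 5.5. No wrongful stop or continuation can be traced from the documents.

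**Conclusion.** The point holds as a drafting error in a safety threshold. In criterion 3 part 1 and the Section 5.5 bullet, the literal text gives the wrong answer at every dose for children of 10 kg or less, and at doses up to 20 mg/day for heavier children. Criterion 29 is self-contradictory. The only entry safety gap is the narrow one above, for children of 10 kg or less; elsewhere the literal entry rule over-excludes. This rests on the literal parse shown and on the intended rule inferred from neighbouring text. The documents give neither a weight distribution nor a count of affected children, so no frequency can be stated. The wording should be corrected, but the trial's conclusions do not depend on it.

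Four stronger readings are tempting and not supported.
- **All three places are inverted.** Criterion 29 is not; it is contradictory.
- **The plan admits immunosuppressed children generally.** The gap is limited by weight, dose, duration and timing, and other criteria still apply.
- **The sentence on higher doses conflicts with criteria 22 and 29 because it names no duration.** It can be read with the preceding bullet or on its own. It is advisory in wording, and Section 5.5 also says that "the decision to continue the subject on trial therapy or vaccination schedule requires the mutual agreement of the investigator, the Sponsor" and the child's representative. That is an ambiguity, not a conflict.
- **The results are affected.** Nothing in the documents links this wording to power, sample size, alpha, the composition of the per-protocol population or a difference between arms.

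**What to change.** In criterion 3 part 1, criterion 29 and the Section 5.5 bullet, delete the words *no more than the equivalent of* and use one rule: *>2 mg/kg/day of prednisone or equivalent, or >20 mg/day if weight is >10 kg, for more than 7 consecutive days*. The sponsor's clinical team should confirm the threshold, because it is inferred from the surrounding text.

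Leave the Section 5.5 sentence on higher doses as it is. Adding the same dose and duration could loosen an existing stop on the second dose after a short high-dose course. The sentence also covers other immunosuppressive agents, to which a prednisone threshold does not apply.

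The cost is the wording of three sentences, by clarification letter or with the next amendment. If the change is judged significant, the Code of Conduct in Section 12.1 requires ethics-board approval before it takes effect. No analysis, power or sample-size text changes.

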5.1.3.1 Subject Deferment Criteria (Before Vaccination 2)

These subject deferment criteria must be reviewed for each subject before Vaccination 2 to ensure that none of the criteria apply to the subject, and/or that Vaccination 2 is deferred for the subject for an appropriate period of time. The subject would only be permitted to continue with a delayed vaccination if the visit can be performed within the allowed window.

The subject should be deferred from continuing in the trial if the subject:

- 19. Has had exposure to varicella or HZ Postvaccination 1 (defer Vaccination 2 until 4 weeks after the exposure):
 - a. Continuous household contact, or
 - b. Playmate contact (generally >1 hour of indoor play), or
 - c. Hospital contact (in same 2- to 4-bed room or adjacent beds in a large ward or prolonged face-to-face contact with an infectious staff member or patient), or
 - d. Contact with a newborn whose mother had onset of chickenpox within ≤ 5 days before delivery or within 48 hours after delivery.
- 20. Has had exposure to measles, mumps, or rubella since Vaccination 1 (defer Vaccination 2 until 4 weeks after exposure).

- 21. Has had recent (within 72 hours) history of febrile illness (≥102.2°F [39.0°C] oral equivalent) before the trial vaccination (defer Vaccination 2 until >72 hours after resolution of febrile illness). Temperature may be converted to oral equivalent by adding 1.0°F to axillary temperatures and subtracting 1.0°F from rectal temperatures.
- 22. Has received any dose of systemic immunomodulatory steroids within 7 days before Vaccination 2 (defer Vaccination 2 until a minimum of 7 days after systemic immunomodulatory steroids).
- 23. Has had any licensed inactivated vaccine administered since Vaccination 1 (defer Vaccination 2 until a minimum of 15 days after nontrial vaccination[s]).
- 24. Has had any licensed live vaccine administered since Vaccination 1 (defer Vaccination 2 until a minimum of 31 days after nontrial vaccination[s]).
- 25. Has had receipt of salicylates (e.g., aspirin or any aspirin-containing products) since Vaccination 1 (defer Vaccination 2 until 14 days after taking medication).
- 26. Has had any medical condition that, in the opinion of the investigator, may interfere with the evaluation of the trial objectives. (The amount of time Vaccination 2 is deferred will be determined by the investigator.)

5.1.3.2 Criteria for Excluding Subjects from Receiving Vaccination 2

These subject exclusion criteria must be reviewed for each subject before Vaccination 2 to ensure that none of the criteria apply to the subject.

The subject must be excluded from receiving Vaccination 2 if the subject:

- 27. Has had any immunoglobulin, nonautologous blood, or blood products administered Postvaccination 1.
- 28. Has had any nontrial measles-, mumps-, rubella-, or VZV-containing vaccine administered Postvaccination 1.
- 29. Has received systemic immunomodulatory steroids (no more than the equivalent of >2 mg/kg total daily dose of prednisone or equivalent or >20 mg/day of prednisone or equivalent for subjects weighing >10 kg) for more than 7 consecutive days Postvaccination 1.
- 30. Has any blood dyscrasias, leukemia, lymphomas of any type, or other malignant neoplasms affecting the bone marrow or lymphatic systems diagnosed Postvaccination 1.
- 31. Has had any acquired or congenital immunodeficiency or active tuberculosis diagnosed Postvaccination 1.
- 32. Has had the occurrence of varicella infection Postvaccination 1.
- 33. Has had a vaccine-related allergic or anaphylactoid reaction reported Postvaccination 1.

- 34. Has enrolled in any other clinical trial other than a surveillance trial Postvaccination 1.
- 35. Has had a seizure, including a febrile seizure, Postvaccination 1.
- 36. Has had thrombocytopenia Postvaccination 1.

